3.4.2 Statistical model

3.4.2.1 Phase lb

An adaptive BLRM guided by the EWOC principle will guide the dose escalation of the combination treatment to its MTD(s)/RP2D(s). A 5-parameter BLRM for combination treatment will be fitted on the dose-limiting toxicity data (i.e. absence or presence of DLT) accumulated throughout the dose escalation, for modeling the dose-DLT relationship of LGX818 (capsule formulation) and MEK162 when given in combination.

The 5 parameter BLRM will be extended to a 10-parameter BLRM to model the dose-DLT relationship of LGX818 (capsule formulation) and MEK162 and LEE011 when given in combination.

Summaries of the posterior distribution of model parameters and posterior distribution of DLT rates based on the DLT data from all patients enrolled in the study and included in the DDS will be produced.

The 5-parameter BLRM (LGX818 and MEK162 original tablet)

The 5-parameter BLRM is formulated in the following way:

Let $\pi_1(d_1)$ be the probability of a DLT if LGX818 is given as a single agent at dose d_1 , and $\pi_2(d_2)$ be the probability of a DLT if MEK162 is given as a single agent at dose d_2 . Both drugs administered to non-fasted patients.

The dose-response relationship is then modeled as:

$$\begin{aligned} \log t(\pi_1(d_1)) &= \log(\alpha_1) + \beta_1 \log(d_1/d_1^*) \\ \log t(\pi_2(d_2)) &= \log(\alpha_2) + \beta_2 \log(d_2/d_2^*) \\ Odds(\pi_{12}(d_1, d_2)) &= \frac{\pi_{12}(d_1, d_2)}{1 - \pi_{12}(d_1, d_2)} = \exp(\eta_{12} \frac{d_1}{d_1^*} \frac{d_2}{d_2^*}) \frac{\pi_1(d_1) + \pi_2(d_2) - \pi_1(d_1)\pi_2(d_2)}{(1 - \pi_1(d_1))(1 - \pi_2(d_2))} \end{aligned}$$

Version 2.2

Confidential

where

- $logit(\pi.(d.)) = log[\pi.(d.)/{1-\pi.(d.)}], \pi(d)$ is the probability of a DLT at dose d.
- $\pi_{12}(d_1, d_2)$ is the probability of a DLT given the combination doses.
- $d_1^* = 100 \text{ mg}$ and $d_2^* = 60 \text{ mg}$ are the reference doses of LGX818 and MEK162 respectively.
- $\alpha_1, \alpha_2, \beta_1, \beta_2 > 0$ and $-\infty < \eta_{12} < \infty$, with η_{12} is the interaction term.

Note that all five parameters α_1 , α_2 , β_1 , β_2 and η_{12} correspond to the effect of the drugs when administered to non-fasted patients.

The 5-parameter BLRM (LGX818 and MEK162 smaller tablet / new tablet variant)

The 5-parameter BLRM is formulated in the following way:

Let $\pi_1(d_1)$ be the probability of a DLT if LGX818 is given as a single agent at dose d_1 , and $\pi_3(d_3)$ be the probability of a DLT if MEK162 is given as a single agent at dose d_3 .

The dose-response relationship is then modeled as:

$$\begin{aligned} \log \operatorname{it}(\pi_1(d_1)) &= \log(\alpha_1) + \beta_1 \log(d_1/d_1^*) \\ \log \operatorname{it}(\pi_2(d_2)) &= \log(\alpha_2) + \beta_2 \log(d_2/d_2^*) \\ Odds\big(\pi_{13}(d_1, d_3)\big) &= \frac{\pi_{13}(d_1, d_3)}{1 - \pi_{13}(d_1, d_3)} = \exp(\eta_{13} \frac{d_1}{d_1^*} \frac{d_3}{d_3^*}) \frac{\pi_1(d_1) + \pi_3(d_3) - \pi_1(d_1)\pi_3(d_3)}{(1 - \pi_1(d_1))(1 - \pi_3(d_3))} \end{aligned}$$

where

- $logit(\pi.(d.)) = log[\pi.(d.)/{1 \pi.(d.)}], \pi(d)$ is the probability of a DLT at dose d.
- $\pi_{13}(d_1, d_3)$ is the probability of a DLT given the combination doses.
- $d_1^* = 100 \text{ mg}$ and $d_3^* = 60 \text{ mg}$ are the reference doses of LGX818 and MEK162 respectively.
- $\alpha_1, \alpha_3, \beta_1, \beta_3 > 0$ and $-\infty < \eta_{13} < \infty$, with η_{13} is the interaction term.

Note that all five parameters α_1 , α_3 , β_1 , β_3 and η_{13} correspond to the effect of the drugs when administered to non-fasted patients.

The 10-parameter BLRM (LGX818 and MEK162 and LEE011)

The 10-parameter BLRM is formulated in the following way:

Let $\pi_1(d_1)$ be the probability of DLT if LGX818 is given as a single agent at QD dose d_1 ,

 $\pi_2(d_2)$ the probability of DLT if MEK162 is given as a single agent at BID dose d₂, and

 $\pi_4(d_4)$ the probability of DLT if LEE011 is given as a single agent at 3 weeks on, 1 week off dose d₄.

The single agent dose-DLT relationships are then modeled as:

Version 2.2

Confidential

LGX818:

 $\operatorname{logit}(\pi_1(d_1)) = \operatorname{log}(\alpha_1) + \beta_1 \, \operatorname{log}(d_1/d_1^r)$

 $\operatorname{logit}(\pi_2(d_2)) = \operatorname{log}(\alpha_2) + \beta_2 \operatorname{log}(d_2/d_2^*)$

LEE011:

 $logit(\pi_{4}(d_{4})) = log(\alpha_{4}) + \beta_{4} log(d_{4}/d_{4}^{*})$

The dose-DLT relationships of the dual combinations of LGX818 + MEK162, LGX818 + LEE011 and MEK162 + LEE011 are modeled as:

$$Odds(\pi_{12}(d_1, d_2)) = \frac{\pi_{12}(d_1, d_2)}{1 - \pi_{12}(d_1, d_2)} = \exp(\eta_{12}\frac{d_1}{d_1^*}\frac{d_2}{d_2^*})\frac{\pi_1(d_1) + \pi_2(d_2) - \pi_1(d_1)\pi_2(d_2)}{(1 - \pi_1(d_1))(1 - \pi_2(d_2))}$$

$$Odds(\pi_{14}(d_1, d_4)) = \frac{\pi_{14}(d_1, d_4)}{1 - \pi_{14}(d_1, d_4)} = \exp(\eta_{14}\frac{d_1}{d_1^*}\frac{d_4}{d_4^*})\frac{\pi_1(d_1) + \pi_4(d_4) - \pi_1(d_1)\pi_4(d_4)}{(1 - \pi_1(d_1))(1 - \pi_4(d_4))}$$

$$Odds(\pi_{24}(d_2, d_4)) = \frac{\pi_{24}(d_2, d_4)}{1 - \pi_{24}(d_2, d_4)} = \exp(\eta_{24}\frac{d_2}{d_2^*}\frac{d_4}{d_4^*})\frac{\pi_2(d_2) + \pi_4(d_4) - \pi_2(d_2)\pi_4(d_4)}{(1 - \pi_2(d_2))(1 - \pi_4(d_4))}$$

The dose-DLT relationship of the triple combination is subsequently modeled as:

where logit(π .(d.)) = log[π .(d.)/{1- π .(d.)}], d₁^{*} = 100mg (QD), d₂^{*} = 60mg (BID) and d₄^{*} = 400mg (3 weeks on, 1 week off) are the reference doses of LGX818, MEK162 and LEE011, respectively, α_1 , α_2 , α_4 , β_1 , β_2 , β_4 > 0 and - ∞ < η_{12} , η_{14} , η_{24} , η_{124} < ∞ are the interaction terms.

Starting dose reassessment

As per [CMEK162X2110-Protocol Amendment 5-Section 6.2.2 Starting dose rationale] for LGX818 and MEK162 and LEE011 triple combination, the Bayesian model will be updated with the most recent data from the ongoing LEE011 single agent trial [CLEE011X2101] and the LGX818 and MEK126 dual combination study [CMEK162X2110], to confirm that the proposed starting dose combination is still appropriate (i.e. satisfies the EWOC criterion) before the first patient is dosed with the triple combination.

[CMEK162X2110-Protocol Amendment 5] did not state information for the dual combinations of MEK162 and LEE011 or LGX818 and LEE011 will be included. However, since these additional studies will provide information on the dose-DLT relationship of the dual combinations, the data for MEK162 and LEE011 under on-going study [CMEK162X2114] and LGX818 and LEE011 under on-going study [CLEE011X2105] have been incorporated. Table 3-1 shows summary of DLT data by study.

Version 2.2

The information from the on-going studies [CMEK162X2114] and [CLEE011X2105] were incorporated through discounting the data directly using the following weight function, w [Neuenschwander (2010)].

$$w = \frac{1}{1 + 2n\tau^2/\sigma^2} = \frac{1}{1 + 2n/n_{\infty}^{\star}}$$

where *n* is the sample size of historical data, σ^2 and τ^2 are the within-trial and between-trial variance. The parameters σ and τ for both of the studies, were set at 2 and 0.5 (correspond to substantial heterogeneity between trials, i.e. $n_{\infty}^* = 16$), respectively. Thus, the weights (*w*) for studies [CMEK162X2114] and [CLEE011X2105] were 0.421 and 0.615, respectively. Table 3-1 shows Prior used for the triple combo.

Correlation
0.233
-0.535
-0.149
NA
NA
NA
NA

Table 3-1Prior used for CMEK162X2110 triple combo (LGX818 + MEK162 +
LEE011)

3.4.2.2 Phase II

Efficacy will be assessed using the local CT/MRI assessments evaluated under RECIST v1.1. The Best Overall Response (BOR) for each patient and individual lesion measurements will be listed. The BOR will be summarized using the Disease Control Rate (DCR) for Phase II arm 1 and the Objective Response Rate (ORR) for Phase II arms 2 + 3 and Phase II arm A.

- The ORR is defined as the proportion of patients with a BOR of CR or PR.
- The DCR is defined as proportion of patients with a BOR of CR or PR or SD.

Both confirmed and unconfirmed summaries will be provided.

Patients who withdrew prematurely due to progression of disease without having any postdose tumor assessment will be classified as treatment failures. Similarly, patients who died due to their disease without having any post-dose tumor assessment will be classified as treatment failures.

ORR and DCR will be provided with their corresponding 95% exact confidence interval according to Clopper-Pearson method [Clopper and Pearson 1934].

3.5 Efficacy evaluation (Secondary Objectives)

Phase lb

Preliminary clinical anti-tumor activity of the combination in patients with BRAF V600 dependent advanced solid tumors will be assessed using the Investigator read CT/MRI assessments evaluated.

ORR will be summarized as point estimate and corresponding 95% exact confidence interval according to Clopper-Pearson method by treatment group. The BOR for each patient and individual lesion measurements will be listed.

Phase II

Local read of CT/MRI assessment will be used for all Phase II efficacy assessments of tumor activity.

Progression-free survival (PFS) will be analyzed using Kaplan-Meier estimates [Kaplan and Meier 1958] (including graphical representation) with 95% confidence interval for median survival.

Overall survival (OS) will be analyzed using Kaplan-Meier estimates with 95% confidence intervals for median survival and survival probabilities for specific time-points (3, 6, 9, 12, 15 and 18 months) will be presented.

Time to response (TTR) and duration of overall response (DOR) will be analyzed using Kaplan-Meier estimate with 95% confidence interval for median survival.

If deem necessary, PFS between the Phase II arm 3 and Phase II arm A may be described in separate analysis plan documentation and displayed external to the main study CSR.

The FAS will be used for all efficacy analyses.

3.5.1 RECIST related endpoints

Response and progression evaluation will be performed according to the RECIST guideline version 1.1 (as described in detail in [CMEK162X2110 Protocol Appendix 14.1]) whenever it applies.

3.5.1.1 Best overall response and other binary endpoints

Best overall response

The Best overall response (BOR) is the best response recorded from the start of the treatment until disease progression/recurrence.

Only overall tumor assessments reported by investigator and performed before the start of any further anti-neoplastic therapies (i.e., any additional secondary anti-neoplastic therapy or surgery) will be considered in the assessment of best overall response.

Confirmation of complete and partial responses (CR and PR, respectively) must be made at least 4 weeks apart. Stable disease must occur > 6 weeks after the start of treatment.

Version 2.2

Confidential

Patients who are of unknown clinical response will be treated as non-responders.

3.5.1.2 Computation of time to event endpoints

Overall survival

Overall survival (OS) is defined as the time from start of treatment to date of death due to any cause. If a patient is not known to have died, survival will be censored at the date of last contact.

As of protocol amendment 10, survival follow-up is no longer performed for patients who have discontinued study treatment in the Phase II part of the study.

Progression free survival

Progression-free survival (PFS) is defined as the time from the date of first study treatment intake to the date of the first documented disease progression or death due to any cause.

By default, if disease progression or death is documented after one single missing tumor evaluation, the actual event date of disease progression/death will be used for the PFS event date. If disease progression or death is documented after two or more missing tumor evaluations, the PFS time of these patients will be censored at the date of the last tumor evaluation with overall lesion response of CR, PR or SD. Patients who begin a new antineoplastic therapy prior to disease progression or death will be censored at the last adequate tumor evaluation prior to the start of the new antineoplastic therapy.

As of protocol amendment 10, post-treatment disease progression follow-up is no longer performed for patients who have discontinued study treatment in the Phase II part of the study.

Time to (overall) response

Time to (overall) response (TTR) will be based on "responders" only and is the time between the date of first treatment administration and the first documented response (CR or PR).

Duration of overall response

Duration of overall response (DOR) will be based on "responders" only and is the time between the date of first documented response (CR or PR) and the date of first documented progression or death due to underlying cancer. If progression or death due to underlying cancer has not occurred, then the patient is censored at the date of last adequate tumor assessment.

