3.5.3 Models and method of analysis

3.5.3.1 Analyses of time-to-event data

The following section presents the general methodology used to analyze time-to-event variables (e.g., PFS, OS, TTR and DOR) for Phase II efficacy assessments of tumor activity.

OS will be analyzed using Kaplan-Meier estimates with confidence intervals for median survival and survival probabilities for specific time-points (3, 6, 9, 12, 15, 18, 21, 24, 27, 30, 33, 36, 39, 42, 45, and 48 months).

PFS will be analyzed using Kaplan-Meier estimates (including plots) with 95% confidence interval for median survival and survival probabilities for specific time-points (3, 6, 9, 12, 15, 18, 21, 24, 27 and 30 months). PFS will be calculated at the MTD/RP2D for Phase II Arm 3 and Phase II Arm A. In addition, for the purposes of the PFS figure, PFS will be calculated for Phase Ib treatment arms as well.

Kaplan-Meier estimates based on all responders with 95% confidence intervals will be presented for TTR and DOR. These two analyses based on responders will be used as a descriptive analysis. Kaplan-Meier estimates with 95% confidence intervals for median TTR and median DOR will be presented. Survival probabilities for specific time-points will include 3, 6, 9, 12, 15 and 18 months for TTR and 3, 6, 9, 12, 15, 18, 21, 24, 27 and 30 months for DOR.

Details on Kaplan-Meier estimates

An estimate of the survival function can be constructed using the Kaplan-Meier (productlimit) method as implemented in PROC LIFETEST.

The median survival is obtained along with 95% confidence intervals as calculated from the PROC LIFETEST output (using method of [Brookmeyer & Crowley, 1982]).

Kaplan-Meier estimates with 95% confidence intervals at specific time points can be summarized. The confidence intervals are constructed using Greenwood's formula for the standard error of the Kaplan-Meier estimate. When the estimated survival function is close to zero or unity, symmetric intervals are inappropriate since they can lead to confidence limits that lie outside the interval [0, 1]. Any limit that is greater than unity will be replaced by 1.0. Any limit that is less than zero will be replaced by 0.0.

Hypotheses and test statistics

Not applicable.

Hazard ratio

Not applicable.

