4.1.1 Tables

Version 2.2

Table 14.1.1.2.1b	Patient disposition by arm	Full Analysis Set	Phase II, Dual Combination
Table 14.1.1.2.1d	Patient disposition by treatment group/arm	Full Analysis Set	Phase Ib/II, Triple Combination
Table 14.1.1.2.2a	Demographics and baseline characteristics by treatment group	Full Analysis Set	Phase lb, Dual Combination
Table 14.1.1.2.2b	Demographics and baseline characteristics by arm	Full Analysis Set	Phase II, Dual Combination
Table 14.1.1.2.2d	Demographics and baseline characteristics by treatment group/arm	Full Analysis Set	Phase Ib/II, Triple Combination
Table 14.1.1.2.3d	Disease history by treatment group/arm	Full Analysis Set	Phase Ib/II, Triple Combination
Table 14.1.3.1d	Relevant medical histories, by primary system organ class, preferred term and treatment group/arm	Full Analysis Set	Phase Ib/II, Triple Combination
Table 14.1.3.2d	Current medical conditions, by primary system organ class, preferred term and treatment group/arm	Full Analysis Set	Phase Ib/II, Triple Combination
Table 14.1.4.1d	Prior antineoplastic therapy – Surgery, by treatment group/arm	Full Analysis Set	Phase Ib/II, Triple Combination
Table 14.1.4.2d	Prior antineoplastic therapy – Radiotherapy, by treatment group/arm	Full Analysis Set	Phase Ib/II, Triple Combination
Table 14.1.4.3d	Prior antineoplastic therapy – Medication, by treatment group/arm	Full Analysis Set	Phase Ib/II, Triple Combination
Table 14.1.4.4d	Prior antineoplastic therapy – Medication, by preferred term and treatment group/arm	Full Analysis Set	Phase Ib/II, Triple Combination
Table 14.1.4.5d	Prior Medications stopped prior to the start of study drug by preferred term, and treatment group/arm	Safety Set	Phase Ib/II, Triple Combination
Table 14.2.1.1d	Summary of best overall response as per local assessment by treatment group/arm	Full Analysis Set	Phase Ib/II, Triple Combination
Table 14.2.2.1b	Analysis of overall survival using Kaplan-Meier method by arm	Full Analysis Set	Phase II, Dual Combination
Table 14.2.2.1d	Analysis of overall survival using Kaplan-Meier method by arm	Full Analysis Set	Phase II, Triple Combination
Table 14.2.3.1b	Analysis of progression free survival as per local assessment using Kaplan- Meier method by arm	Full Analysis Set	Phase II, Dual Combination
Table 14.2.3.1d	Analysis of progression free survival as per local assessment using Kaplan- Meier method by arm	Full Analysis Set	Phase II, Triple Combination

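### Amendment 10 ends survival follow-up for Phase II patients off treatment only, yet OS is still censored at last contact with landmarks to 48 months, so late OS estimates risk upward bias of a size the SAP does not bound.

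*SAP*

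**What the plan says.** Section 3.5.1.2 defines the endpoint: "Overall survival (OS) is defined as the time from start of treatment to date of death due to any cause". Its censoring rule is: "If a patient is not known to have died, survival will be censored at the date of last contact". The next paragraph records the change in follow-up: "As of protocol amendment 10, survival follow-up is no longer performed for patients who have discontinued study treatment in the Phase II part". The PFS paragraph carries a parallel note: "As of protocol amendment 10, post-treatment disease progression follow-up is no longer performed for patients who have discontinued study treatment".

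On reporting, section 3.5.3.1 requires OS "survival probabilities for specific time-points (3, 6, 9, 12, 15, 18, 21, 24, 27, 30, 33, 36, 39, 42, 45, and 48 months", whereas section 3.5 says "survival probabilities for specific time-points (3, 6, 9, 12, 15 and 18 months) will be presented". Section 4.1.1 keeps "Analysis of overall survival using Kaplan-Meier method by arm" in the final CSR for Phase II, once for the dual combination (Table 14.2.2.1b) and once for the triple (Table 14.2.2.1d). Section 1.5 places the final cut-off at or after the point when every patient has completed or discontinued.

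The SAP sets no common OS censoring date, no limit on the landmarks, and no sensitivity analysis or caveat for the change in follow-up. Section 2.1.2.10 contains only a general promise of suitable methods for censored data. The SAP gives neither the date of amendment 10 nor the number of Phase II patients who were then alive and off treatment.

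**The concern.** Had follow-up ended for everyone on one calendar date, the censoring would be administrative and Kaplan-Meier would be sound. Here it ends by treatment status. After the amendment, only patients still on treatment are systematically observed for death, and each of them leaves the risk set soon after stopping. Because the final cut-off waits until everyone is off treatment, this applies to every patient who stops after the amendment.

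Section 1.1 has patients treated until progression, unacceptable toxicity or withdrawal of consent, with treatment beyond progression allowed in some circumstances. Stopping is thus linked to prognosis, and a higher death hazard afterwards is a reasonable expectation. Kaplan-Meier then gives censored patients the lower risk of those still on treatment, and the late part of the estimate is pulled upward. At stake are the late OS probabilities by arm in the final CSR, which readers may take as evidence of long-term survival.

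**Working it through.** The SAP states no OS rate, event count or follow-up figure, so there is nothing to reproduce. The check asks how large the effect could be on assumed inputs.

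**Assumptions (none from the SAP).** Uniform entry over 12 months; median 11 months on treatment; median survival after stopping 9 months; on-treatment death hazard h of 0, 0.005 or 0.01 per month; amendment 10 at calendar month 24, 36, 48 or 60 from first entry. Under the planned rule, a patient off treatment is censored at the later of the amendment date and one month after stopping, and a patient on treatment is followed on. Kaplan-Meier was run on 400,000 simulated patients per scenario.

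**True OS in closed form.** With a = ln 2/11 = 0.0630 and b = ln 2/9 = 0.0770,

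S(t) = e^(−(a+h)t) + a·[e^(−(a+h)t) − e^(−bt)]/(b − a − h).

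For h = 0 this is (b·e^(−at) − a·e^(−bt))/(b − a). At 48 months: (0.0770 × 0.0486 − 0.0630 × 0.0248)/0.0140 = 0.156. The simulated true value is also 15.6%.

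**48-month OS under the planned rule (excess over true, in points)**

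| Amendment at month | h = 0 (true 15.6%) | h = 0.005 (true 13.2%) | h = 0.01 (true 11.3%) |
|---|---|---|---|
| 24 | 53.5% (+37.9) | 43.6% (+30.4) | 35.2% (+23.9) |
| 36 | 32.8% (+17.2) | 27.0% (+13.8) | 22.5% (+11.2) |
| 48 | 18.9% (+3.3) | 15.8% (+2.6) | 13.2% (+1.9) |
| 60 | no difference | no difference | no difference |

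**Earlier landmarks, h = 0.** With the amendment at month 24, 18-month OS is 66.5% against a true 64.5% (+2.0), and 36-month OS is 56.4% against 28.8% (+27.6). With the amendment at month 36, 18 and 24 months show no difference. With it at month 48, 36 months shows none.

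**When the effect vanishes.** A landmark is safe once every patient has reached it before the amendment. For 48 months that means accrual + 48: here 12 + 48 = month 60.

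**Second set of inputs.** Entry over 18 months; h = 0.005; medians on/after treatment of 12/12, 6/9 or 18/12 months. The 48-month excess is:
- amendment at month 30: +16 to +25 points (for example 0.458 against 0.203);
- month 42: +4.5 to +12 points;
- month 60: 0 to +0.5 point (the last entrants have only 60 − 18 = 42 months);
- month 84: zero.

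**Conditions that remove it.** In the second set at month 42, if half of later deaths are still recorded the excess falls to +0.3 to +3.6 points; if all are, it is about zero. With equal hazards on and off treatment it is zero (0.248 against 0.249).

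**Common cut-off.** Censoring every patient at the amendment date recovers true OS at the landmarks it supports. In the 12/12 case, month 42 gives 0.342 against 0.342 at 36 months, and month 60 gives 0.203 against 0.204 at 48 months.

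**The case against.** A reader might infer that late OS in this trial is biased upward, that the medians are too, and that PFS suffers similarly. The documents do not support that.

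- **Timing.** The SAP does not date amendment 10. The dual-combination interim cut-off is 31 August 2015, and the change log moves from June 2015 to September 2022. A late amendment, with little or no effect, fits the text as well as an early one.
- **Hazards and capture.** The largest figures assume no deaths on treatment, which maximises the contrast with off-treatment risk. Treatment beyond progression is allowed, so patients on treatment are not simply those doing well. Later deaths might also still reach the database.
- **Medians.** A median that all patients had passed before the amendment is unaffected.
- **PFS.** Patients who stop for progression already have their event. Only those who stop without it lose assessments, and no size has been shown.
- **Weight.** OS is secondary and single-arm, and section 3.5.3.1 marks hypothesis tests and hazard ratios as not applicable. No primary endpoint or dose decision depends on it. The SAP also states the follow-up change directly below the OS definition.

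All of this stands, and it limits the size and weight of the point. It does not remove the mechanism: the SAP records follow-up that depends on treatment status, leaves the estimator unchanged, and asks for landmarks to 48 months.

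**Conclusion.** The concern holds as a risk, not as a demonstrated bias. Phase II OS landmarks not reached by all patients before amendment 10 are exposed to upward bias if the death hazard is higher off treatment than on and later deaths are not otherwise captured. On the first set of assumed inputs the 48-month excess runs from about 24 to 38 points (amendment at month 24), through 11 to 17 (month 36) and 2 to 3 (month 48), to zero from month 60. The SAP cannot say where in that range the trial lies; the sponsor, who knows the date, can.

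The conflict between sections 3.5 and 3.5.3.1 matters here, because it decides how much late OS is reported. If the 18-month list governs, exposure is much smaller. The point should be fixed before the final CSR, but it does not threaten the primary conclusions.

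**What to change.** In section 3.5.1.2, for the Phase II OS tables (14.2.2.1b and 14.2.2.1d):

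1. State the date amendment 10 took effect, per site if dates differ, and the number of Phase II patients then alive and off treatment.
2. Censor every patient known to be alive on that date at that date, and do not use later deaths or contacts. Patients last contacted earlier stay censored at last contact.
3. Report only landmarks that this follow-up supports, with numbers at risk.
4. Label any OS estimate under the current last-contact rule as supplementary, with a note on the change in follow-up.
5. Reconcile the OS landmark lists in sections 3.5 and 3.5.3.1.
6. Optionally, apply the same cut-off as a PFS sensitivity analysis, without claiming a size for the PFS effect.

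The cost is SAP wording and one derived date. Some late on-treatment follow-up and the latest landmarks are lost. If the amendment came late, the results will barely change.

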Table 14.2.4.1d	Analysis of time to response as per local assessment using Kaplan-Meier method by arm	Full Analysis Set	Phase II, Triple Combination, Confirmed Responders
Table 14.2.5.1b	Analysis of duration of response as per local assessment using Kaplan- Meier method by arm	Full Analysis Set	Phase II, Dual Combination, Confirmed Responders
Table 14.2.5.1d	Analysis of duration of response as per local assessment using Kaplan- Meier method arm	Full Analysis Set	Phase II, Triple Combination, Confirmed Responders
Table 14.3.1.1.1d	Dose limiting toxicities occurring during the first 28 days by primary system organ class, preferred term and treatment group	Dose Determining Set	Phase Ib, Triple Combination
Table 14.3.1.2.1d	Treatment-emergent adverse events (all causality) by preferred term, maximum grade (grades 1-4) and treatment group/arm	Safety Set	Phase Ib/II, Triple Combination
Table 14.3.1.2.2a	Treatment-emergent adverse events (all causality) by preferred term, maximum grade (overall and grade 3/4) and treatment group	Safety Set	Phase Ib, Dual Combination
Table 14.3.1.2.2b	Treatment-emergent adverse events (all causality) by preferred term, maximum grade (overall and grade 3/4) and arm	Safety Set	Phase II, Dual Combination
Table 14.3.1.2.2d	Treatment-emergent adverse events (all causality by preferred term, maximum grade (overall and grade 3/4), and treatment group/arm	Safety Set	Phase Ib/II, Triple Combination
Table 14.3.1.2.3d	Serious adverse events (all causality) by preferred term, maximum grade (overall and grade 3/4), and treatment group/arm	Safety Set	Phase Ib/II, Triple Combination
Table 14.3.1.2.4a	Treatment-emergent adverse events leading to permanent study drug discontinuation (all causality) by preferred term, maximum grade (grades 1-4) and treatment group	Safety Set	Phase Ib, Dual Combination
Table 14.3.1.2.4b	Treatment-emergent adverse events leading to permanent study drug discontinuation (all causality) by preferred term, maximum grade	Safety Set	Phase II, Dual Combination

Pfizer Inc.

	(grades 1-4) and arm		
Table 14.3.1.2.4d	Treatment-emergent adverse events leading to permanent study drug discontinuation (all causality)by class, preferred term, maximum grade (grades 1-4) and treatment group/arm	Safety Set	Phase Ib/II, Triple Combination

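### Duration of response censors responders who die of causes other than their cancer, unlike PFS, and so can overstate DOR if such deaths occur

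*SAP*

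**What the plan says.** SAP Section 3.5.1.2 (Computation of time to event endpoints) runs DOR, in responders only, from the first documented CR or PR to "the date of first documented progression or death due to underlying cancer". The censoring rule follows: "If progression or death due to underlying cancer has not occurred, then the patient is censored at the date of last adequate tumor assessment".

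The same section runs PFS from first study treatment intake to "the date of the first documented disease progression or death due to any cause". It then adds two censoring rules for PFS. A progression or death found after two or more missing tumor evaluations is censored at the last evaluation showing CR, PR or SD. A patient who starts new antineoplastic therapy before an event is censored at the last adequate evaluation before that therapy. The DOR paragraph states neither rule.

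Section 3.5.3.1 names the estimator: "Kaplan-Meier estimates with 95% confidence intervals for median TTR and median DOR will be presented". It adds DOR probabilities at time points from 3 to 30 months and gives the status of the responder analyses: "These two analyses based on responders will be used as a descriptive analysis".

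Section 4.1.1 lists Table 14.2.5.1b, "Analysis of duration of response as per local assessment using Kaplan- Meier method by arm", for the Phase II dual combination, and Table 14.2.5.1d for the Phase II triple combination. Both are in confirmed responders.

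**The concern.** A responder who dies of toxicity, infection or a cardiac event without progressing has a PFS event but is a censored observation for DOR. Kaplan-Meier assumes that a censored patient carries the same future risk of progression as those still followed. A patient who has died can no longer progress, so this death is a competing event rather than lost follow-up. The SAP gives no reason for the narrower DOR event, no rule for attributing cause of death, no competing-risk estimator and no all-cause version of DOR.

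Two things are at stake. First, deaths attributed to causes other than the cancer, including any attributed to treatment, cannot shorten the reported durability of response. Second, the DOR and PFS tables for the same arms rest on different event and censoring rules, so a reader cannot reconcile them patient by patient.

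**Working it through.** **No planned figure to reproduce.** The SAP states no expected DOR, event count or precision for DOR. The check is therefore one of direction and plausible size.

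**Inputs from the SAP.** DOR event and censoring rules and PFS event rule: Section 3.5.1.2. Kaplan-Meier as the only estimator: Section 3.5.3.1. Spacing of tumor assessments: 56 days, from Day 56 to Day 112 in Table 2-1.

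**Assumptions, not in the SAP.** Constant hazards; an all-cause median DOR of 10 months; a share f of first response-ending events that are non-cancer deaths, taken from 0 to 20%.

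**Step 1, direction.** Let λ be the all-cause hazard of losing response. Non-cancer deaths occur at rate fλ and the events that DOR counts occur at rate (1-f)λ. With non-cancer deaths censored, Kaplan-Meier estimates exp(-(1-f)λt). The all-cause curve is exp(-λt). For f > 0 the first lies above the second at every t > 0; for f = 0 they coincide.

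**Step 2, median.** All-cause median = ln2/λ. Median under the SAP rule = ln2/((1-f)λ). The ratio is 1/(1-f).

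**Step 3, 12-month probability.** All-cause: 0.5^(12/10) = 0.435. SAP rule: 0.5^(1.2(1-f)).

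| f | 1/(1-f) | Median under SAP rule (all-cause 10.0 months) | 12-month DOR under SAP rule (all-cause 43.5%) |
|---|---|---|---|
| 0 | 1.00 | 10.0 | 43.5% |
| 2% | 1.02 | 10.2 | 44.3% |
| 5% | 1.05 | 10.5 | 45.4% |
| 10% | 1.11 | 11.1 | 47.3% |
| 20% | 1.25 | 12.5 | 51.4% |

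**Step 4, allowing for scan timing.** The closed form ignores that progression is seen only at scans and that censoring falls at the last scan. A Kaplan-Meier simulation added both, with 400,000 responders per setting, 56-day scans and an assumed 30-month cut-off.

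| f | 12-month DOR, all-cause | 12-month DOR, SAP rule | Median, all-cause (months) | Median, SAP rule (months) |
|---|---|---|---|---|
| 0 | 0.464 | 0.464 | 11.04 | 11.04 |
| 2% | 0.465 | 0.473 | 11.04 | 11.04 |
| 5% | 0.463 | 0.482 | 11.04 | 11.04 |
| 10% | 0.462 | 0.501 | 11.04 | 12.88 |
| 20% | 0.459 | 0.542 | 11.04 | 12.88 |

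The direction agrees. The simulated median moves only in steps of 56/30.4375 = 1.84 months, so it does not change for f up to 5% and then jumps one step. The landmark probabilities show the effect more smoothly.

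**Step 5, the two missing rules.** These have no single direction. Without the new-therapy rule, a progression after new therapy counts as a DOR event that PFS would censor, which shortens DOR; a response that continues on the new therapy adds event-free time, which lengthens it. Without the two-missed-evaluation rule, a late-detected progression becomes an event, but at a late date. The SAP gives no basis for sizing either. Section 3.5.1.1 already excludes assessments after further antineoplastic therapy from best overall response, so the plan recognises the issue elsewhere.

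**The case against.** A reader might infer that DOR is inflated and that it contradicts PFS. The SAP supports neither.

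- **Contradiction.** DOR and PFS are separately named endpoints, each with its own explicit event rule. Nothing says that DOR is PFS restricted to responders. A cancer-specific DOR is a narrower definition, and the text is unambiguous. This objection stands: what is missing is a reason and an all-cause version, not internal consistency.
- **Inflation.** There is none unless a responder dies of another cause before progression, and the SAP gives no such share. At f of 2 to 5% the closed-form shift is 2 to 5%, and the simulated median does not move. This stands as a limit on size, not on direction.
- **Carried to death as still responding.** One might suppose that the patient is counted as responding up to the death date. The rule censors at the last adequate assessment. The bias comes from losing an event, not from adding time.
- **Visibility.** Deaths by primary reason (Tables 14.3.2.2.2b and 14.3.2.2.2d) and all-cause PFS by arm (Tables 14.2.3.1b and 14.2.3.1d) are planned. They help, but they are not restricted to responders and do not give an all-cause DOR.
- **Consequence.** DOR is secondary (Table 1-1) and descriptive, and Section 3.5.3.1 plans no hypothesis test or hazard ratio. This stands.
- **Comparability.** Section 1.5 says that this SAP also describes the interim CSR for the dual combination, with a cut-off of 31 August 2015. Replacing the definition outright could leave the final dual-combination DOR not comparable with the interim one. This stands and shapes the fix.

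**Conclusion.** The point holds in a limited form. As written, non-cancer deaths without progression are handled as non-informative censoring in DOR but as events in PFS, with no stated reason and no all-cause DOR. If such deaths occur among responders, this rule moves the Kaplan-Meier DOR estimate upward. Under constant hazards the median is multiplied by 1/(1-f): about 2 to 5% for f of 2 to 5%, 11% at 10%, nothing at 0. Both f and the 10-month median used in the working are assumptions.

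The absent new-therapy and missed-evaluation rules are a separate gap. They leave DOR and PFS unreconciled but cannot be cited as further overstatement, because they can act in either direction. No test, error rate or decision rule depends on DOR, so this is a cheap improvement rather than a threat to a trial conclusion.

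**What to change.** In Section 3.5.1.2, define DOR for Tables 14.2.5.1b and 14.2.5.1d as the time from first documented response to first documented progression or death from any cause. State that the PFS rules for new antineoplastic therapy and for two or more missing evaluations also apply to DOR.

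Keep the present cancer-death-only definition, with its current censoring, as a labelled sensitivity analysis, so that the dual-combination result can still be set beside the interim CSR. A footnote giving the number of responders in each arm who died of another cause without progression would let the reader see how much of any difference is due to this rule.

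The cost is a short text change and one extra analysis per table. The event and censoring dates are already derived for PFS. The headline DOR may be slightly less favourable.
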